4.7 Risks of Harm/Potential for Benefits to Subjects

A. Description of Risks of Harm to Subjects

- Reasonably Foreseeable Risks of Harm
 - (1) Phone Screen and Questionnaire Completion: Potential participants may become uncomfortable or distressed when asked certain questions (e.g., regarding illicit substance use; current/past mental health and physical health). However, [name] has many years of experience administering these questionnaires in various study protocols and study personnel will receive extensive training in conducting the Phone Screen. Also, participants will be offered an additional layer of protection via a Certificate of Confidentiality.
 - (2) HRVB: There are some minimal risks associated with the administration of the proposed breathing intervention. The most often observed risk is discomfort breathing at a pace that is much slower than typical, and worry that one is not inhaling adequate air. To address this potential risk, study clinicians will be carefully trained in providing participants with a clear rationale for the procedure, clinical management of distress associated with the intervention, and appropriate adjustments to ensure participants are able to adhere to the protocol.

9/17/2024

- (3) Physiological Recording: All of our sensors record responses from the surface of the body and are hence noninvasive, and should not cause the participants any discomfort or physical harm. Patients may experience mild discomfort with the application and removal of passive electrodes to monitor their physiological parameters at in person sessions. However, we do not anticipate this discomfort to be longstanding. To minimize discomfort, all sensors are placed and removed by study staff that will receive training in appropriate placement and removal. Study personnel will train participants in the lab and during remote sessions on proper placement and removal of the Inner Balance ear clip sensor.
- (4) Assessment Procedures: No risks are associated with self-report or behavioral assessments other than mild distress due to the sensitive nature of questions or induced distress as a function of difficulty or attention demands on some of the behavioral tasks. Study personnel are experienced and sensitive to this issue and will cease testing if a participant displays excessive frustration during behavioral testing, although the PI has never experienced this in her prior research.
- (5) Nicotine Replacement Therapy: The transdermal nicotine patch is available over-the-counter, has been widely used, and its risks are minimal. Possible adverse side effects of the nicotine patch include abnormal redness of the skin, itching, headache, insomnia, diarrhea, indigestion, and nervousness. We minimize risks by screening patients for contraindications of nicotine patch use and requiring physician concurrence. In addition, participants will be queried regarding craving and side effects to ensure adequate dosing and to reduce adverse effects. Participants who are started at 14mg will be moved up to 21mg if they report strong cravings, whereas those started at 21mg will be stepped down to 14 if they report the nicotine to be uncomfortably stimulating.
- (6) Breach of Confidentiality: There is a risk that confidential information about a participant may be revealed. Although all technology that is incorporated in the study is encrypted and HIPAA compliant, reliance on teletherapy introduces risks such as: participants not having access to a confidential and isolated location in which to conduct teletherapy sessions and potential identifiable information collected in conjunction with using data from the Inner Balance and iCOquit ® Smokerlyzer devices. This could conceivably result in discriminatory action against participants by insurers, employers, or other groups. However, as an additional layer of protection, a Certificate of Confidentiality has been automatically awarded by NIH.
- Risk of Harm from an Intervention on a Subject with an Existing Condition N/A

Other Foreseeable Risks of Harm

Our research team employs standard procedures to ensure confidential information about study participation is not disclosed. All data are linked to an arbitrary 3-digit study ID unrelated to personal information. The file linking participants to their study ID will be stored in a password-protected file, located within a password-protected database on an encrypted computer and maintained separately from de-identified personal data files. Only select trained laboratory personnel will have access to the file. All computer files or printed data used for analysis also will be de-identified. Consent forms and payment forms will be stored in a locked file cabinet separate from data in an office that is locked when not occupied. Participants' confidentiality also is protected by never associating a participant's name with results in any published or otherwise publicly presented report. Demographic information, including information about participants' age, ethnicity, education, marital status and employment status, will be reported using averages and percentages computed over multiple participants

9/17/2024

and never reported at the level of individual participants. In addition, all participants will be explicitly instructed to not modify any iCOQuit, Inner Balance, smartphone, and tablet device and application settings or include any identifiable information within these devices and applications (See Section E. Minimizing Risks of Harm for additional detail).

Observation and Sensitive Information

- B. Procedures which Risk Harm to Embryo, Fetus, and/or Pregnant Subjects
- C. Risks of Harm to Non-Subjects

D. Assessment of Social Behavior Considerations

Study risks are minimal and include a small, temporary increase in distress as a result of the assessments; however, the methodologies employed have been utilized in many labs and clinical settings with hundreds of participants suffering from a range of psychopathology, and approved by as many IRBs.

E. Minimizing Risks of Harm

Participants who indicate psychological distress during participation will be provided with several strategies to reduce distress as needed, including, distraction and deep breathing. Staff will conduct a thorough risk assessment with participants who report suicidal ideation or intent.

Any participants who report suicidal ideation or intent will be provided with information and phone numbers for three local options for mental health care: Rutgers University Behavioral Health Care [contact]), Rutgers Health Psychiatry/Psychology Clinic [contact]), and the Rutgers Psychological Clinic in [contact]). In the unlikely event that a participant reports an imminent intent to harm themselves, we will contact Acute Psychiatric Services [contact]).

Certificate of Confidentiality

Participants will additionally be protected via a Certificate of Confidentiality issued by the Department of Health and Human Services. The Certificate will protect the investigators from being forced to release research data that contains identifiable information about participants, even under a court order or subpoena. The certificate does not protect the investigators from being compelled to make disclosures that: (1) have been consented to in writing by the participants or the participant's legally authorized representative, (2) are required by the Federal Food, Drug, and Cosmetic Act (21 U.S.C. 201 et seq.) or regulations issued under that Act, or (3) have been requested from a research project funded by NIH or DHHS by authorized representatives of those agencies for the purpose of audit or program review. The Certificate will protect study personnel located at Rutgers University as well as consultants affiliated with the proposed project from disclosing information. The Certificate will additionally protect the privacy of participants by withholding their names and other identifying characteristics from all persons not connected with the conduct of that research.

Provisions to Protect Confidentiality on Study Devices

All participants will be explicitly instructed to not modify or include any identifiable information within the iCOQuit, Inner Balance, smartphone, and tablet device settings. Upon return, a lab personnel member will connect all used iCOQuit and Inner Balance devices to a lab smartphone to confirm that no identifiable information is present upon device retrieval and will restore all default settings before the devices are provided to a new participant. For lent smartphones and tablets, all identifiable information will be cleared by lab personnel upon device retrieval and will be re-checked again before being given to a new participant. Our lab will also implement a used/clean technology device clearing system. Specifically, returned technology (i.e., iCOQuit, Inner Balance, Smartphone, or Tablet) will be placed in the "used" bucket. Once all protection provisions have been employed, the device will then be placed in the "clean" bucket. This system will increase ease of redistributing reusable tech devices,

9/17/2024

identifying those that need to be wiped, and ensureg that redistributed devices are free of PHI.

Provisions to Protect the Privacy Interests of Subjects

Participants will be asked to engage with trained research staff throughout the course of the study. However, if participants indicate a desire not to work with a particular staff member, we will oblige. In addition, potential participants will not interact with any member of the study team that they have a personal or professional relationship with.

Provisions to Protect from Exposure to Contaminants

All used iCOQuit, Inner Balance, smartphone, and tablet devices will be thoroughly cleaned with a sanitization wipe upon device retrieval before being given to a new participant to reduce the spread of person-to-person contaminants.

F. Potential Benefits to Subjects

The SCT treatment including the NRT patch is associated with improved smoking cessation outcomes, which may have a long-term positive impact on health and psychological well-being. In addition, though this study is exploratory in nature and benefits of HRVB have not yet been assessed in daily smokers, we are hopeful that participants receiving HRVB will experience additional reductions in anxiety and depressive symptoms, and improved physiological health as determined by indices of autonomic balance.

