by the research team remotely to assess intervention fidelity. HeartMath has a history of working with researchers conducting clinical trials of HRVB. The Inner Balance software was selected for this trial given its usability, portability, and cost-effectiveness.

Homework Practice: Participants will be asked to practice HRV biofeedback 20 minutes daily, in bouts of 5 minutes. Practicing for 20 minutes a day is necessary to most optimally train the reflexes that will help participants control stress response, cravings, and many other symptoms related to the autonomic nervous system (Lehrer, Vaschillo, & Zucker, 2013). In addition to verifying practice outside of intervention sessions, the Inner Balance device allows the investigators to download biofeedback data for quality assessment. Participants will also be prompted via Metricwire, a separate web-based platform developed for ecological momentary assessment [EMA], to provide ratings of cigarette craving and withdrawal, as well as relaxation and distress, on a 100-point scale both before and after completing daily respiratory training practice. This system is accessed using a free smartphone app, which allows the study team to acquire daily diary data from a participant's smartphone and is secure, private, and HIPAA compliant. The Metricwire app will additionally be used to remind participants to practice on three occasions per day; this reminder will include information regarding their potential compensation for completing their respiratory training practice. Participants will have the option to immediately complete EMA prompts, and subsequently practice, or to complete ratings at a later time. Participants may also open the app on their own (i.e., self-initiated) to complete ratings at their own convenience. The goal of incorporating EMA data collection is to promote homework completion, increase adherence to and engagement with the assigned intervention, and provide quantitative data regarding the relation between breathing practice and craving, withdrawal, relaxation, and distress while minimizing data-entry error or recall bias. All participants will use *Metricwire*. If participants do not have a smartphone which supports the study apps, a smartphone will be loaned to them for the duration of their study participation.

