Five remote respiratory training sessions and four remote SCT sessions will occur. During HRVB respiratory training sessions, participants will be instructed to use the Inner Balance device and smartphone applications while simultaneously sharing their screen via Zoom while additionally attending the Zoom session on their laptop or tablet. Therapists will provide real time feedback and instruction during the session while assessing their progress via screenshare and while viewing the participant through their laptop/tablet. SCT sessions will also occur via Zoom.

| Week | Session | Core Components | Time | Pay |
|------------------------------------|----------|--|------|-------------------------|
| Week 1a ^L (Baseline) | Screener | Consent, questionnaires, assess abstinence via CO scheduling, set quit date | 30 | \$35 (if ineligible) |
| | IA | Recording session: Baseline, Plain Vanilla, Dot Tracking | 50 | |
| (Session 1) | SCT S1 | SCT program introduction and orientation to Clear Pathways Goals: Understanding why you smoke, health effects of smoking/quitting, reasons to quit, assess and build confidence | 30 | \$10 |
| | HRVB S1 | Intervention Overview Recording session Goal: Introduce HRVB Breathing using pacer and Inner Balance | 60 | |
| | ЕМА | Introduction/enrollment to homework | | |

9/17/2024

| | | | T | 1 |
|---|---------|---|----|--------------------------------|
| Week 1b ^v | SCT S2 | Goals: Review quit date, plan for quit day (week 2), troubleshoot potential barriers to quitting Introduce NRT and instructions on how to use the patch | 30 | \$10 |
| | HRVB S2 | Biofeedback practice session Goal: Introduce biofeedback Assign homework: Practice 4x/day for at least 20m | 30 | |
| | ЕМА | Assess homework compliance and surveys cravings, withdrawal, distress, and relaxation symptoms | | |
| Week 2 ^v (Quit Day) | SCT S3 | Review homework Goals: Continue to discuss and revise quit plan, monitor motivation to quit, trouble-shoot/learn from failures | 30 | \$10 |
| | HRVB S3 | Biofeedback practice session Goal: Review and adjust Inner Balance HRVB Assign homework: Practice 4x/day for at least 20m | 30 | |
| | ЕМА | Assess homework compliance and surveys cravings, withdrawal, distress, and relaxation symptoms | | up to \$105 for HW practice |

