| Bedfont handheld piCO Smokerlyzer and iCOquit Śmokerlyzer, which will be used for in-person and remote verification, respectively. Daily Information Sheet: Details participants' cigarette use, alcohol consumption, substance use, medications, meals consumed, and NRT-related side effects Craving/Withdrawal Visual Analog Scale (CW-VAS): Measures X X X X X X | | | | - | | | - |
| will be used for in-person and remote verification, respectively. Daily Information Sheet: Details participants' cigarette use, alcohol consumption, substance use, medications, meals consumed, and NRT-related side effects Craving/Withdrawal Visual Analog Scale (CW-VAS): Measures X X X X X X X | | | | | | | |
| Daily Information Sheet:Details participants' cigarette use, alcohol consumption, substance use, medications, meals consumed, and NRT- related side effectsXXXXCraving/Withdrawal Visual Analog Scale (CW-VAS):MeasuresXXXX | | | | | | | |
| consumption, substance use, medications, meals consumed, and NRT-related side effects Craving/Withdrawal Visual Analog Scale (CW-VAS): Measures X X X X | | X | X | X | X | X | X |
| related side effects Craving/Withdrawal Visual Analog Scale (CW-VAS): Measures X X X X | | | | | | | |
| Craving/Withdrawal Visual Analog Scale (CW-VAS): Measures X X X X X | | | | | | | |
| | | | X | X | X | X | X |
| | | | _ | _ | | | |

| (none or non-existent) to 100 (extreme). | | | | | |   |
|---|---|---|-------|-----|-----|----------|
| Timeline Followback: Used to assess ongoing cigarette, e-cigarette, | X | X | X | X | X | X |
| patch, alcohol, and other tobacco and substance use (Sobell & Sobell, 1992 & 1995). | | | | | | |
| Positive and Negative Affect Schedule: Used to assess current | X | X | X | X | X | X |
| emotional states before and after intervention sessions (Watson & Clark, | | | | | | |
| 1988 & 1999). | | | \ \ \ | \ \ | - V | - V |
| Felt Arousal Scale (FAS): Used to measure activation on a 6-point | X | X | X | X | X | X |
| scale from low (1 point) to high arousal (6 points) (Svebak & Murgatroyd, 1985). | | | | | | |
| Distress Intolerance Index: Used to assess participants' perceptions | X | | | | X | X |
| of their ability to tolerate mental distress (McHugh & Otto, 2011). | | | | | ^ | ^ |
| Short-form Health Survey (SFH): Used to assess quality of life in | Х | | X | X | Х | X |
| regard to health (Ware, Kosinski, & Keller, 1996). | | | | | | |
| Thoughts about Abstinence: Used to assess commitment to | Х | | Х | Х | Х | X |

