HRVB and SCT Clinician Training and Supervision: Clinicians will receive a minimum of 8 hours of training from study investigators in the application HRVB and will have to complete a minimum of 5 practice sessions prior to seeing participants. Clinicians will be approved for the study following careful assessment of their protocol adherence, competent application of skills, by the PI. Clinicians will have to demonstrate general knowledge in appropriately modifying HRVB for participants, navigating and addressing common barriers (e.g., discomfort, dizziness), addressing motivation and adherence, instructing and monitoring participants both in-lab and virtually, and will role-play managing several common issues that arise during HRVB before they are assigned participants. Fidelity data will be collected via independent evaluators who will use an HRVB-specific rating scale to assess protocol adherence, implementation of strategies and skills in-session. Designated study assessors will be asked to code audio-recordings, specifically, 25% of the initial eight HRVB sessions provided to participants will be coded (Muse & McManus, 2013). Fidelity will additionally be assessed by Co-I [name] who will review recorded physiological data from baseline and 3-month follow up to rate whether participants, under therapist instruction, received adequate resonance between heart rate and blood pressure, central to the success of the intervention. Measures of treatment fidelity are critical to the current proposal given it has never been applied to smokers and requires ongoing monitoring of participant behavior and physiology. For example, slow-paced breathing is sometimes accompanied by compensatory changes in breath depth, a process that can inadvertently decrease end tidal carbon dioxide (etCO2), which is contraindicated and will not result in desired RSA oscillations; clinicians will need to know how to identify and remedy contraindicated breathing patterns, such as hyperventilation, both during in-lab and remote sessions, to promote accurate HRVB application.

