The ongoing COVID-19 pandemic places all research in an unpredictable situation. We anticipate that we may experience challenges in recruitment and retention associated with illness or safety concerns that could affect both study personnel and participants. We will address these issues on an ad hoc basis, for example, by subbing in respiratory therapists when possible, permitting participants to do make-up sessions, collecting in-person data at modified times, etc., and carefully documenting each adjustment made. Also, a growing body of empirical work has documented the extensive effects of the pandemic on mental health, including emotional distress and substance use. We have added several questionnaires, both validated quantitatively and qualitatively, to obtain information regarding the effects of the pandemic on mental health and functioning, as well as information regarding personal COVID-19 related experiences (e.g., disease contraction by self or close contact). Collection of this data will help the study team glean whether any related effects, or lack thereof, or differences in outcomes between Stage 1A and 1B may be attributable to the pandemic.

Transition to a remote intervention introduces several concerns related to intervention fidelity. Although the Inner Balance device provides relatively reliable real time HRVB feedback, therapists cannot view the participant and their physiology simultaneously. This may introduce challenges in determining whether the participant is practicing the intervention correctly and troubleshooting difficulties they are experiencing, such as feeling breathless or lightheaded. To address these concerns, the baseline appointment includes extensive training in the intervention and orientation to using the Inner Balance device and the Zoom mobile and computer software, so that participants can swiftly move between screens when working with their respiratory therapist remotely. Also, it is possible that the intervention may be disrupted due to connectivity problems. In the event this occurs, a backup plan, including the use of other HIPAA compliant platforms (e.g., Microsoft Teams), will be enacted, or the session will be moved to traditional audio phone call or rescheduled.

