- Consent form language: Our consent form will include language notifying participants that information on the clinical trial, including a description and results, will be posted at ClinicalTrials.gov.

Results information: In accord with this policy, we will ensure that results are reported at ClinicalTrials.gov within 12 months of the primary completion date – i.e., the date that the final subject follow-up, or final, data collection point. Results to be reported by the indicated policy deadline will include participant flow (e.g., recruitment details), demographic and baseline characteristics (e.g., race/ethnicity, sex/gender, age, cigarettes smoked daily), key outcome measures and analyses, serious and other adverse events, and limitations and caveats.

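### No listed home-practice rating or side-effect query asks about breathing symptoms, although the protocol names them as HRVB risks and most prescribed breathing is done alone at home

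*Combined protocol and SAP*

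**What the plan says.** **Named risks.** Section 4.7 A(2): "The most often observed risk is discomfort breathing at a pace that is much slower than typical". The same sentence mentions a fear of not getting enough air. Section 1.3 (Clinician Training and Supervision) lists discomfort and dizziness as common barriers. It warns that slow breathing can "inadvertently decrease end tidal carbon dioxide (etCO2), which is contraindicated", and requires clinicians to recognise hyperventilation. Section 1.3 (Potential Problems and Alternative Strategies) adds breathlessness and light-headedness in remote delivery. The stated response is clinician training and adjustment of the technique.

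**What is asked.** Around home practice, Metricwire prompts participants "to provide ratings of cigarette craving and withdrawal, as well as relaxation and distress, on a 100-point scale", before and after. These ratings are a condition of practice payment. The Daily Information Sheet in Table 2 covers cigarette use and alcohol "consumption, substance use, medications, meals consumed, and NRT-related side effects". The side-effect queries in Table 1 (week 3) and in 4.7 A(5) also concern nicotine replacement.

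**What is promised.** Under 6.4 Reporting Results, the registry entry will include "serious and other adverse events". Sections 4.4 and 6.7 refer to an attached data and safety monitoring plan (DSMP), which is not part of the supplied text.

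**Remote observation.** Section 1.3 (Remote Intervention Sessions) has therapists giving feedback "while assessing their progress via screenshare and while viewing the participant through their laptop/tablet". Potential Problems and Alternative Strategies states that "therapists cannot view the participant and their physiology simultaneously", and allows a fall-back to an ordinary audio call.

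**The concern.** Acceptability and feasibility of HRVB are the primary aim. The listed side-effect questions cover the patch, which is background treatment, and not the breathing intervention under test. Events that are asked about are recorded more completely than events that must be volunteered. A table built from these instruments could therefore show patch effects and few breathing effects because of how the questions were put. The result would feed the decision on a larger trial and a public adverse-event report. With a form limited to nicotine replacement, a breathing symptom might also be left out or filed under the patch.

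**Working it through.** **1. Routes by which a breathing symptom could be recorded**

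| Route (section) | Reaches home practice? | Asks about a breathing symptom? |
|---|---|---|
| Metricwire pre/post ratings (1.3) | Yes | No; generic distress only |
| Daily Information Sheet (Table 2) | Not described as a home diary; marked at study assessment points | No; nicotine replacement only |
| Side-effect queries (Table 1 week 3; 4.7 A(5)) | Not about breathing practice | No; nicotine replacement only |
| Acceptance and Feasibility Ratings (Table 2) | No; negative feelings in session | No |
| HRVB session trouble-shooting (Table 1) | Indirectly | Unstructured |
| Pre/post-session affect ratings, progress notes (2.2) | Indirectly at most | No item; free text |
| Structured adherence questions (2.2) | Yes, but only below 75% compliance | Aimed at adherence |
| Exit interview (Table 2) | Possibly, once at 3 months | Overall feedback |

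The recordings listed in 1.3 do not include etCO2, so over-breathing has to be seen or reported.

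**2. Volume of home practice, checked against the plan's own pay figures**

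Inputs: up to $15 a day in weeks 2-6; $10 for each of six sessions; $35 at baseline and at 1 month; $50 at 3 months; $50 bonus (Table 1, 1.3, 4.6).

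- Per week: 7 x $15 = $105, as stated.
- Total: 5 x $105 + 6 x $10 + 2 x $35 + $50 + $50 = $755, as stated.

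The paid period is therefore 5 x 7 = 35 days. At 20 minutes a day in 5-minute bouts (1.3, Homework Practice), that is 35 x 20 = 700 minutes, or 140 bouts.

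**3. Supervised time**

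Seven HRVB sessions, the first of 60 minutes and six of 30-40 minutes (1.3): 60 + 6 x 30 = 240, to 60 + 6 x 40 = 300 minutes.

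**4. Home share = home / (home + supervised)**

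| Adherence | Home min | With 240 supervised | With 300 supervised |
|---|---|---|---|
| 100% | 700 | 700/940 = 74% | 700/1000 = 70% |
| 75% | 525 | 525/765 = 69% | 525/825 = 64% |
| 50% | 350 | 350/590 = 59% | 350/650 = 54% |

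Home practice stays the majority unless adherence falls below 240/700 = 34% to 300/700 = 43%. Counting every session minute as breathing understates the home share. So does reading Table 1's homework line as 20 minutes a day in total.

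**5. Illustration of under-counting**

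The documents give no symptom rate and no capture rate, so both are assumed here. Suppose 20% of 30 participants have a breathing symptom. The expected number recorded is 30 x 0.20 x capture, and the chance of recording none is (1 - 0.20 x capture)^30.

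| Capture | Expected recorded | Chance of none |
|---|---|---|
| 100% | 6 | 0.1% |
| 50% | 3 | 4% |
| 30% | 1.8 | 16% |

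Even with full capture, 0 of 30 leaves a one-sided 95% upper bound of 1 - 0.05^(1/30) = 9.5%.

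**The case against.** The strongest reply is that adverse-event collection is deferred to the DSMP, which section 6.7 says the funder approved. It may solicit breathing symptoms. This stands: the finding can cover only the instruments listed in the supplied text.

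Second, the home rating does include distress before and after practice, and 4.7 A(2) itself speaks of distress associated with the intervention. A rise from before to after is a repeated, practice-linked signal. This stands in part. Practice in weeks 2-6 spans quit day and the weeks after it, so the score mixes breathing symptoms with withdrawal, and it misses a participant who is light-headed but not distressed.

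Third, trouble-shooting in sessions, affect ratings, questions below 75% compliance, downloaded practice data and the exit interview give further routes. They are real but partial. None is a systematic symptom question, and the compliance trigger passes over a symptomatic participant who keeps practising.

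Fourth, the primary outcomes are attendance, minutes, ratings and technical problems, not a side-effect count. Poor tolerability could still show as fewer minutes or lower ease. This is fair, but a low ease score does not say why.

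A reader might go further and infer that breathing events will be recorded only if volunteered, that home practice carries no symptom signal at all, or that HRVB will certainly look better tolerated than it is. The documents do not support these readings, because of the distress rating, the partial routes and the unseen DSMP. The home share also measures exposure, not missed events.

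**Conclusion.** The gap is real and should be closed. The listed home-practice ratings and side-effect queries have no breathing-symptom item, while the protocol names such symptoms as HRVB risks. Under-counting relative to patch events is likely, not established, and its size cannot be derived from the documents. The conclusion assumes that the DSMP adds no solicited breathing item, and the exposure share assumes the prescribed minutes or the stated adherence range. The conflict over what remote therapists can see is a separate inconsistency; it does not itself show that home data are missing.

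**What to change.** 1. Add one item to the post-practice Metricwire rating: breathlessness or air hunger, and dizziness or light-headedness, each with a severity grade.
2. Widen the side-effect wording on the Daily Information Sheet to cover breathing as well as nicotine replacement. This complements item 1 and cannot replace it, because the sheet is marked at study assessment points.
3. In 1.6 and 6.5, tabulate both descriptively as HRVB tolerability: number and percent of participants, and of rated practices, by severity.
4. Alternatively, show that the DSMP already collects this and cite the form.
5. Reconcile the two statements in 1.3 on whether remote therapists see participant and physiology together, and flag audio-only sessions in the data.

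If data collection has ended (recruitment was planned through March 2023), code the session recordings and progress notes for breathing symptoms, state the limitation and carry the item into the larger trial.

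The cost is one extra tap per practice, one wording change and one table, with no new visit or device. Asking systematically will raise the count of mild events, and the report should say so.
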